Northwestern University Feinberg School of Medicine
Department of Anesthesiology
Protocol

Title: Incidence of Post-Dural Puncture Headache following Unintentional Dural Puncture: A Randomized Trial of Intrathecal Morphine versus Saline

Principal Investigator: [name]. **Co-investigator (s):** [name]

Affiliation: Department of Anesthesiology
Northwestern University Feinberg School of Medicine

Institution: Northwestern Memorial Hospital

Research Aims:

- 1. Research Questions(s):** Does the administration of intrathecal morphine after delivery reduce the risk of post-dural puncture headache (PDPH) following unintentional dural puncture (UDP) with a 17-g Tuohy needle in obstetric patients?
- 2. Hypotheses:** Intrathecal morphine decreases the incidence of PDPH as compared to placebo after UDP with a Tuohy needle in obstetric patients.

Background: Unintentional dural puncture is a known risk of neuraxial techniques, occurring in roughly 1% of all epidural catheter placements.¹⁻³ The incidence of PDPH after unintentional dural puncture is 50-80%.³⁻⁵ The International Headache Society has defined PDPH as a headache that occurs following a dural puncture, worsens within 15 minutes after sitting or standing and improves within 15 minutes after lying, with at least one of the following: neck stiffness, tinnitus, hypacusia, photophobia, or nausea. The headache develops within 5 days after dural puncture and resolves either spontaneously within 1 week or within 48 hours after effective treatment of the spinal fluid leak (usually by epidural blood patch).⁶ PDPH can be a significant cause of maternal morbidity in the obstetric patient. In addition to interfering with the mother's ability to care for her newborn, treatment of PDPH can increase health care costs by prolonging the length of hospitalization and number of emergency room visits.⁷

Several strategies exist to treat PDPH, but currently there are no proven interventions for preventing or reducing the likelihood of PDPH following unintentional dural puncture.^{8,9} Previously investigated strategies include prophylactic epidural blood patch, the use of intrathecal (IT) catheter with delayed removal, intrathecal saline injection and infusion, and cosyntropin administration.¹⁰⁻¹⁵ Retrospective and observational studies have demonstrated a decrease in PDPH rates following unintentional dural puncture when intrathecal catheters are placed instead of subsequent placement of an epidural catheter.^{1,12} Other observational studies have examined the use of intrathecal opioids to reduce the incidence of PDPH.^{14,16} Recently, one randomized controlled trial explored the use of epidural morphine for the prevention and treatment of PDPH with positive results. Al-metwalli showed a decrease in the PDPH rate from 48% to 12% after administration of epidural morphine 3 mg at the time of delivery and again at 24 hours postpartum.¹⁷ Administration of epidural morphine following UDP may produce unpredictable central nervous system side effects, however, as a large dural hole may facilitate intrathecal translocation of epidural morphine, increasing the risk of respiratory depression. At our institution, it is common practice for an intrathecal catheter to be placed after UDP instead of an epidural catheter at another spinal level. Given that the administration of epidural morphine after known UDP may have unpredictable effects and that the use of intrathecal catheters following UDP is a common practice, we feel it is necessary to study the use of intrathecal morphine administration following UDP to decrease the incidence of PDPH. In our randomized prospective study, the rates of PDPH following unintentional dural puncture with placement of an intrathecal catheter will be compared in two groups: intrathecal morphine versus intrathecal saline

administration 1-2 hours after delivery followed by immediate catheter removal. We have chosen to administer intrathecal morphine 150 µg as this is the current dose given to parturients receiving morphine via spinal administration for Cesarean delivery and has a predictable side effect profile and history of safety in this population. The dose roughly corresponds to the epidural morphine dose administered by Al-metwalli in his randomized controlled trial.¹⁷

The incidence of PDPH has been estimated to approximately 50% after unintentional dural puncture.¹⁸ Assuming that a decrease of at least 50% would be necessary to suggest a clinical utility of this treatment, we determined that a sample size of 64 patients in each group would be required to achieve an 80% power to detect this difference between epidural and intrathecal catheter. Group sample sizes of 64 achieve 80% power to detect a difference between the group proportions of 0.25. The proportion in group one (the treatment group) is assumed to be 0.5 under the null hypothesis and 0.25 under the alternative hypothesis. The proportion in group two (the control group) is 0.5. The test statistic used is the two-sided Fisher's exact test. The significance level of the test was targeted at 0.05. The significance level actually achieved by this design is 0.03. Sample size was calculated using PASS 11, version 11.0.01, release date 11/3/2010 (NCSS Inc. Kaysville, UT). To account for protocol exclusions and patients lost to follow-up, 170 patients will be randomized. Recruitment for this project will take roughly 1-2yrs.

2. Patient entry, exclusion and dropout criteria:

Inclusion: Postpartum patients following vaginal delivery with an unintentional dural puncture and functioning intrathecal catheter. Patients must be 18 years of age or older and English speaking.

Exclusion: Previous PDPH, body mass index BMI>40 kg/m², obstructive sleep apnea (OSA), morphine allergy and patients who receive Cesarean delivery (as these patients would all receive intrathecal morphine and could therefore not be randomized).

3. Protocol specific methods: Eligible patients will be asked by anesthesia personnel to participate in this study shortly following delivery when the nurse taking care of the patient deems the patient appropriate for discharge. Informed, written consent will be obtained and the pharmacy on the 10th floor Prentice Women's Hospital will determine group allocation by randomization table. The patient will be randomized to one of two groups: intrathecal morphine (treatment) vs. saline (control) which will be administered through the existing intrathecal catheter. Patients randomized to the treatment group (morphine) will receive preservative-free morphine 0.3 mL (150 mcg) intrathecally. Those randomized to the control group will receive normal saline 0.3 mL intrathecally. The drugs will be prepared in syringes by a pharmacist on the 10th floor Prentice Women's Hospital and labeled as "IT morphine study drug." The anesthesiologist injecting the study drug, the study nurse collecting follow-up data, and the patient will be blinded to group assignment. After thoroughly sanitizing the catheter port with a Chloroprep wipe and allowing adequate time for drying of the Chloroprep, the anesthesiologist will first attach a 3-mL syringe to the catheter port and aspirate to a volume of 1 mL. This syringe will then be removed from the port. The study drug will then be administered through the intrathecal catheter via the tuberculin syringe. The 3-mL syringe containing the aspirate will then be injected via the catheter, effectively flushing the study drug through the catheter. The intrathecal catheter will be removed immediately following the injection. If the anesthesiologist is unable to aspirate from the catheter, the intrathecal drug will be administered and flushed with 1.0 mL of preservative free saline to ensure drug delivery. The inability to aspirate will be noted on the data sheet at the time of administration. Sterile gloves will be used for all morphine or saline administration.

After administration of intrathecal morphine, all patients will have their respirations monitored every hour for a period of 12 hours and then every two hours for a period of 12 hours. This is standard protocol after the administration of neuraxial morphine at NMH. If the patient develops symptoms of nausea, vomiting, urinary retention or pruritus, she will receive standard interventions per the NMH order-set for neuraxial opioids.

On postpartum days 1-5, all patients will be visited daily while inpatient and called by phone after discharge from the hospital. The following information will be also recorded in this study: presence or absence of PDPH (as defined by the International Headache Society), signs and symptoms of cranial nerve injury, the patient's verbal rating score for pain (VRSP, 0-10 scale), current headache treatments including oral analgesics, intravenous caffeine, or epidural blood patch, side effects of intrathecal morphine (respiratory depression, nausea, vomiting, pruritus, urinary retention. Patients who develop a headache will be followed for 3 days after the resolution of their headache. Physician observers will make treatment recommendations according to the following protocol (previously described by Scavone et al, 2004¹⁵): Mild postural headaches (defined as VRSP <4) will be treated with conservative therapy including oral hydration, increased oral caffeine intake, and oral analgesics as needed. Moderate postural headaches (defined as VRSP 4-6 without limitation of childcare ability) will also receive conservative therapy. Patients with moderate postural headaches limiting childcare abilities, and patients complaining of severe postural headaches (defined as VRSP >6) will be advised to undergo a therapeutic epidural blood patch (EBP). This treatment will consist of the epidural injection of 20 mL of autologous blood over 2 to 3 min through the epidural needle, injected at the level of the presumed UDP or one level below. The patient will be positioned in the sitting position for the procedure and then repositioned supine for a period of 1 hour after the epidural blood injection. The EBP will not be performed for at least 24 hours after dural puncture. If the EBP fails to relieve the headache after 24 hours, or if the headache recurs after successful treatment, the EBP may be repeated. The protocol outlined above follows standard procedure at NMH.

4. Risks/Benefits:

Risks to study patients include: itching, nausea, vomiting, urinary retention, constipation, dizziness, hypotension, depression of cough reflex and slowing of respirations. The rare risk is respiratory depression leading to respiratory arrest.

The presumed risks are similar to that assumed by any parturient who receives spinal morphine for Cesarean delivery, which is common practice. To minimize the risk of apnea, patient will be monitored postpartum in the same manner that patients receiving neuraxial morphine for Cesarean delivery are routinely monitored as described above.

If any patient experiences nausea, vomiting or pruritus, she will be treated with medications based on the clinical scenario as evaluated by the attending anesthesiologist on duty who will not be blinded to treatment group. There is also a risk of loss of confidentiality.

Confidentiality: Access to electronic data is computer password protected. All data will be deleted from the password protected computer 5 years after manuscript preparation. Electronic and paper documents will be destroyed using current technology. The paper documents will be shredded using the current vendor for HIPAA sensitive documents using the current technique.

Data Analysis:

1. **Data collection form:** Data collection form attached.

2. **Data evaluation:** The primary outcome is the incidence of PDPH. The intrathecal morphine and saline groups will be compared using the Fisher's exact test. The clinical characteristics of the study groups will be compared between groups using the Mann Whitney test for interval and continuous data and a χ^2 statistic for nominal data. Secondary outcomes include severity of headache, need for epidural blood patch, rate of neuraxial infection, neuraxial complications. $P < 0.05$ will be required to reject the null hypothesis.

3. Interpretation of Anticipated Results: A reduced incidence of PDPH in the intrathecal morphine group without an unacceptable incidence of side effects would support the effectiveness of its administration after UDP.

Budget:

- 1. Materials:** Preservative free morphine (2-mL) 1000 microgram ampule – cost 80 cents per vial for 64 patients. Preservative free 0.9% saline (10-mL) vial – cost 35 cents per vial for 64 patients. The total cost for study drugs is \$74.75, which will be provided by the Department of Anesthesiology.
- 2. Labor Requirements:** Obstetric anesthesiology research nurses and obstetric anesthesiology fellows will recruit patients for the study and will perform all data collection.
- 3. Presentation Cost:** This project will be presented at a national meeting such as ASA or SOAP.

Consent: *(Provide a consent form in the relevant IRB format. The template for these forms can be found on the Web at: <http://www.research.northwestern.edu/opr5/irb/templates/>)*

Additional information for preparation of an IRB Submission:

NA

Incidence of post-dural puncture headache following unintentional dural puncture: a randomized trial of intrathecal morphine vs. saline

DATA COLLECTION FORM

Study Number: _____

Date: _____

EGA: _____

Parity: _____

Height (inches): _____

Weight (kilogram): _____

Procedure performed by: _____

If resident/fellow specify level of training PGY- _____

Loss of Resistance - air / saline

Dural puncture interspace - _____

Intrathecal Catheter Placement: Date _____ Time _____ Location (skin) ____ cm

Intrathecal Catheter Removal: Date _____ Time _____ Location (skin) ____ cm

Total infusion dose: _____ mLs

Mode of delivery - Vaginal / Forceps or Vacuum Assisted

Start of pushing - _____ End of pushing - _____

Delivery time - _____ Time of removal of catheter _____

Aspirate of CSF prior to drug administration - yes / no

Incidence of post-dural puncture headache following unintentional dural puncture: a randomized trial of intrathecal morphine vs. saline

Patient Study Number _____

Postpartum day # _____

Evaluator: _____

Date: _____ Time: _____ Presence of PDPH yes / no
If yes, Headache VPRS score (1-10): 0 1 2 3 4 5 6 7 8 9 10

Current Headache therapy (please circle and specify doses when appropriate)

1. Hydration _____
2. Oral analgesics _____
3. IV analgesics _____
4. IV Caffeine _____
5. Epidural blood patch date - _____
(please fill out EBP data sheet with details)

Headache VPRS score after treatment _____

Cranial nerve involvement - yes / no

If yes, please specify _____

Presence of backache - yes / no

Backache VPRS score 0 1 2 3 4 5 6 7 8 9 10

Signs/symptoms of infection

1. Max Fever in last 24hours _____
2. Superficial (i.e., swelling, redness, purulence around site) yes / no What? _____
3. CNS (i.e., meningitis, epidural abscess) _____

Lower extremity peripheral nerve symptoms

1. Weakness (where) _____
2. Paresthesia (where) _____

Recommended Therapy (please circle all that apply)

1. Hydration
2. Oral analgesics
3. IV analgesics
4. IV Caffeine
5. Epidural blood patch

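### Does an undefined allowance for exclusions after randomisation leave the primary Fisher comparison open to bias?

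*Combined protocol and SAP*

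**What the plan says.** The sample-size paragraph (Methods, Size of study groups) asks for 64 per group for 80% power to detect 50% against 25% PDPH with a two-sided Fisher's exact test. On error rates it says "The significance level of the test was targeted at 0.05" and "The significance level actually achieved by this design is 0.03". It then inflates: "To account for protocol exclusions and patients lost to follow-up, 170 patients will be randomized".

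The next item is headed "Patient entry, exclusion and dropout criteria", but only inclusion and exclusion lists follow.

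Under Protocol specific methods, eligible patients are approached after delivery and consent, and the pharmacy then "will determine group allocation by randomization table". Treatment is described for patients according to the group they were randomised to. If the catheter cannot be aspirated, the study drug is still given and the event is recorded. On masking: "The anesthesiologist injecting the study drug, the study nurse collecting follow-up data, and the patient will be blinded to group assignment". Daily follow-up on postpartum days 1 to 5 covers all patients.

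Risks/Benefits says that nausea, vomiting or pruritus will be treated on the judgement of "the attending anesthesiologist on duty who will not be blinded to treatment group".

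The primary analysis, under Data evaluation, is brief: "The intrathecal morphine and saline groups will be compared using the" Fisher's exact test. No analysis set is named, and nothing is said about patients whose PDPH status is unknown.

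**The concern.** The inflation applies to patients already randomised, and it names exclusions separately from loss to follow-up. Ordinary screening failures cannot be meant, because they would not require more patients to be randomised. Every listed exclusion (previous PDPH, BMI above 40, sleep apnoea, morphine allergy, Cesarean delivery) can also be known before the pharmacy allocates. The phrase therefore seems to foresee removals after allocation on grounds the plan does not give, and the heading that promises dropout criteria supplies none.

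If removal is related to both arm and outcome, the Fisher comparison is biased and its error rate is no longer controlled. If removal is unrelated to both, only power is lost. With no definition, no named decision-maker and no as-randomised statement, a reader of the plan cannot say in advance which applies. The unblinded attending anesthesiologist looks like one route by which knowledge of the arm could enter.

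**Working it through.** **Inputs.** From the sample-size paragraph: rates 0.50 and 0.25, two-sided Fisher's exact test at 0.05, 64 per group, 170 randomised. Equal allocation is assumed from the equal groups, giving 85 per arm. All results below come from full enumeration of two independent binomials, counting tables with Fisher p ≤ 0.05.

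**The plan's own figures.** At 64 per arm, power is 0.802 and the achieved error rate at 50% in both arms is 0.0298, matching the stated 80% and 0.03. At 63 per arm power is 0.794, so 64 is the smallest adequate of the sizes enumerated (60 to 66).

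**The margin.** 2 × 64 = 128; 170 − 128 = 42; 42/170 = 24.7%.

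**Error rate under removal.** Assume no true effect (50% in both arms) and remove k patients per arm whose PDPH rate is r. The rate among those kept is (42.5 − k·r)/(85 − k). For k = 21 and r = 0.70 this is (42.5 − 14.7)/64 = 0.434; for r = 0.30 it is (42.5 − 6.3)/64 = 0.566. The removal rates are assumptions, chosen to span mild to severe selection.

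| Removed per arm | Neutral (50/50) | 70% in both arms | 70% morphine, 50% saline | 70% morphine, 30% saline |
|---|---|---|---|---|
| 5 | 3.2% | 3.2% | 3.5% | 4.1% |
| 10 | 4.1% | 4.1% | 5.2% | 8.5% |
| 21 | 3.0% | 3.4% | 8.1% | 24.5% |

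The neutral column varies because the test is discrete. Removal related to outcome but not to arm (third column) does no harm. With 10 removed per arm, selection in one arm only takes the rate to 5.2%, essentially nominal. The 24.5% needs the whole margin of 42 spent on exclusions, none on loss to follow-up, with headache cases preferentially dropped from the morphine arm and preferentially kept in the saline arm.

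**Power with everyone kept as randomised.** For 0.50 against 0.25, power is 0.802 at 64 per arm, 0.863 at 75, 0.883 at 80 and 0.901 at 85. Suppose (assumption) that 10% of the morphine arm get no drug and keep a 50% rate. The morphine rate becomes 0.9 × 0.25 + 0.1 × 0.50 = 0.275, and power is 0.822 at 85 per arm, 0.776 at 75 and 0.702 at 64. With 20% untreated the rate is 0.30 and power at 85 is 0.715.

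**What the text allows.** Four features bear on whether removals could be many and differential.

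- Arm membership is set by randomisation, and nothing suggests regrouping by treatment received.
- Entry requires a functioning catheter, and eligibility and consent precede allocation, so late discovery of ineligibility should be uncommon.
- The one deviation foreseen, failed aspiration, leads to the drug being given and a note being made, not to removal.
- Follow-up is of all patients, with no condition on compliance.

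**The case for a change.** The strongest opposing case is that the plan budgets for up to one patient in four leaving after allocation, and that Data evaluation, the whole analysis plan, does not say who stays in. Failed aspiration makes delivery of the drug less certain, and investigators could decide after the fact whether such patients count. Morphine side effects are recorded at follow-up, so a link between arm and withdrawal is conceivable. A sentence or two would settle the matter at almost no cost.

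The textual part stands: the exclusions are undefined, no analysis set is named, and unknown PDPH status is not addressed. The step from silence to bias does not stand. The unblinded attending has one documented role, treating side effects, and no passage gives that person a say in exclusions or in diagnosing PDPH. The people who inject, who collect follow-up and who report symptoms are all blinded.

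Nor is a strict rule free of cost. Keeping untreated patients in dilutes the effect, so sizing the inflation for missing outcomes alone would not secure 80% power: 64 observed per arm with 10% of the morphine arm untreated gives 70.2%. The existing margin is useful cover for loss and dilution together.

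**Conclusion.** No change is called for. The plan omits detail that a competent analyst supplies by default: every randomised patient with a known PDPH status is counted in the assigned arm, and any removals are reported with reasons. Read that way, the comparison is sound, with 90.1% power if all 85 per arm are observed and 82.2% if 10% of the morphine arm go untreated. The stated 80% is therefore kept only while loss and dilution are both small.

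The error rate stays at or below 4.1% with 5 removals per arm in every scenario tried, and is 5.2% with 10 per arm and selection in one arm. Material inflation needs removals that are both numerous and differential, and no passage describes or permits removal by arm or outcome. The heading that mentions dropout criteria without giving any is a clerical slip.

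This conclusion rests on 1:1 allocation (inferred), on the illustrative removal and non-treatment rates, and on the described blinding being kept. It would need another look if the trial report showed many exclusions after randomisation, unevenly spread between the arms.

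### Five intrathecal-morphine side effects are to be recorded and the conclusion depends on them, but the attached form has no field for any of them and Data evaluation names none

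*Combined protocol and SAP*

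**What the plan says.** The commitment is in Methods 3 (Protocol specific methods), in the paragraph on postpartum days 1-5. Among the data to be recorded in the study it lists "side effects of intrathecal morphine (respiratory depression, nausea, vomiting, pruritus, urinary retention". The same section says that "the study nurse collecting follow-up data, and the patient will be blinded to group assignment", and Budget 2 says that research nurses and fellows "will recruit patients for the study and will perform all data collection".

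Data Analysis 1 identifies the instrument in four words: "Data collection form attached".

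Data Analysis 2 gives Fisher's exact test for PDPH, and the Mann-Whitney and chi-square tests for clinical characteristics. It then states: "Secondary outcomes include severity of headache, need for epidural blood patch, rate of neuraxial infection, neuraxial complications".

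Data Analysis 3 sets the condition for a favourable reading: "A reduced incidence of PDPH in the intrathecal morphine group without an unacceptable incidence of side effects would support the effectiveness".

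Two passages describe routine care that touches these effects. Methods 3 sets this schedule for every participant: "have their respirations monitored every hour for a period of 12 hours and then every two hours for a period of 12 hours". Risks/Benefits says that treatment for nausea, vomiting or pruritus depends on the clinical scenario as "evaluated by the attending anesthesiologist on duty who will not be blinded to treatment group".

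**The concern.** The text and the form disagree. The text promises five side effects; the page that the nurse fills in each day does not ask for any of them. The form is not short on safety in general: it covers cranial nerve signs, backache, fever, superficial and CNS infection, and leg weakness or paresthesia. What it leaves out is the set of expected effects of the drug being randomized.

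A daily collector works from the page in hand. Nausea or itching that is not asked about at the contact cannot be recovered at analysis. The trial would then report its benefit from blinded, scheduled assessments and its side effects from whatever happened to be charted, although its own interpretation needs both.

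**Working it through.** The main check is a comparison of text, form and analysis section; the plan states no figure on this point to reproduce.

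**Data items in Methods 3 against the form**

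| Item to be recorded | Field on the form |
|---|---|
| PDPH present or absent | yes |
| Cranial nerve injury | yes |
| Verbal pain score | yes, though the headache score is asked only if PDPH is present |
| Current headache treatment | yes |
| Side effects of intrathecal morphine | no |

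Four of the five items have a field, one of them conditional.

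**The five side effects against form and analysis**

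| Effect | Form field | Named in Data evaluation |
|---|---|---|
| Respiratory depression | no | no |
| Nausea | no | no |
| Vomiting | no | no |
| Pruritus | no | no |
| Urinary retention | no | no |

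That is 0 of 5 on the form and 0 of 5 in Data evaluation. The form has no general adverse-event line. The one other sheet it cites is for blood-patch details.

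**What routine care could supply**

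- Respiratory depression: scheduled observation for 12 h + 12 h = 24 h.
- Nausea, vomiting, pruritus and urinary retention: Methods 3 mentions only standard treatment if symptoms develop. No scheduled enquiry is described outside the study contacts.
- No section names the chart as a study data source.

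**Time window**

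The Background puts dosing 1-2 hours after delivery, and study contacts begin on postpartum day 1. Fever, over the last 24 hours, is the only item on the daily page with a look-back window. New fields therefore need their own window, or symptoms in the first hours after dosing could be missed even if the fields are added.

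**What complete data would show (scale only)**

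The documents give no side-effect incidences, so those below are assumptions, rounded to whole patients. Intervals are Newcombe 95% CIs for the risk difference. The first column of results uses the planned 64 per arm. The second uses 85 per arm (170/2), assuming that everyone randomized is dosed and assessed.

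| Assumed incidence | 64 per arm | 85 per arm |
|---|---|---|
| 5% v 5% | 3 v 3 events: half-width 8.8 points | 4 v 4: 7.4 points |
| 30% v 10% | 19 v 6: 6.6 to 33.4, half-width 13.4 | 26 v 8: 9.2 to 32.6, half-width 11.7 |
| 50% v 50% | 32 v 32: half-width 16.8 | 42 v 42: 14.7 |

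With zero events in an arm, the one-sided 95% upper limit is 1 − 0.05^(1/n): 1 − 0.05^(1/64) = 4.6%, or 1 − 0.05^(1/85) = 3.5%.

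These figures do not measure the defect. They show that complete data would be informative about common effects and weak for rare ones, so descriptive reporting is the reasonable aim.

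**The case against.** The strongest reply is that the plan already has a commitment, a contact schedule and a blinded collector, so all that is missing is a line on a form. This is right as far as it goes. A reader might infer that the trial does not intend to collect side effects; Methods 3 says the opposite. The gap is between that intention and the instrument.

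A second reply is that the secondary-outcome list is open-ended and that neuraxial complications are undefined, so side effects may be covered. They are indeed not ruled out, and no listed secondary outcome has its own named test. But an open list names no side effect and puts no field on the form.

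Third, the chart may hold the information. It may, in part. A reader might go further and infer that an unblinded attending assesses the side-effect outcomes. The documents do not say so: Risks/Benefits has that attending choose treatment, for three of the five effects, and respiration is observed on a fixed schedule. The narrower point stands: charted treatment for those three would carry the influence of an unblinded decision.

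Fourth, a reader might set 24 hours of respiratory monitoring against follow-up to day 5 and see a shortfall. Nothing in the documents says that these effects of a single dose are expected through day 5, so that contrast is not part of the point.

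Finally, asking about opioid effects could hint at allocation. That is true, but the commitment in Methods 3 already accepts this risk, and the order of questions can reduce it.

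**Conclusion.** The point holds as an inconsistency between protocol and form, with a matching gap in the analysis section. None of the five promised side effects has a form field and none is named in Data evaluation, while the stated interpretation turns on their incidence. It should be fixed before enrolment, or as soon as possible if enrolment has begun, because data not collected at the contact are lost.

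The conclusion assumes that the form is used as attached and that no separate side-effect page exists. If one does, citing it would settle the collection part and leave only the reporting sentence to add.

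The consequence is confined to the side-effect half of the conclusion. A reader might infer that the PDPH result is compromised; it is not, because PDPH has its own daily field, a blinded nurse and a named test. The plan also does not say how an unacceptable incidence will be judged. That is missing detail rather than part of the contradiction, but incidences by arm with intervals would at least let readers judge for themselves.

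**What to change.** 1. **Form.** Add to the daily page a yes/no field for each of the five effects, asked as since study drug at the first contact and since last contact thereafter. The blinded nurse completes these after that day's PDPH assessment has been written down.
2. **Data source.** State that the existing hospital respiratory monitoring record is the source for respiratory depression in the first 24 hours, extracted in the same way in both arms. The monitoring sentence refers to all patients but opens with the administration of morphine, so confirm that the record exists for saline patients too.
3. **Data evaluation.** Add a sentence such as: Respiratory depression, nausea, vomiting, pruritus and urinary retention will each be reported by arm as the number of patients with at least one event, with risk difference and 95% CI, as descriptive safety data supporting the interpretation in Data Analysis 3.

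The cost is five fields, two sentences, a slightly longer contact and a small extra table. The residual downside is that answers about opioid effects may hint at allocation before the next day's PDPH assessment; recording PDPH first protects the same day's judgement but not fully the later ones. No change is needed to the sample size, the primary analysis or clinical care.
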